6. STUDY PARAMETERS/ENDPOINTS

a. Primary study endpoint

Incidence of rt-PCR-confirmed SARS-CoV2 infection following BCG vaccination compared to that following placebo.

b. Secondary study endpoint

In individuals who test positive for Covid-19, the proportion with severe disease following BCG vaccination compared to placebo, as defined by the following necessary care levels: non-hospital care; patient hospitalized but no oxygen required; hospitalized and oxygen required; patient treated in intensive care and/or on mechanical ventilation; patient died.

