Participants will complete intermittent surveys via an electronic system every 7 days to assess the presence of any flu-like symptom, including sore throat, fever, headache, malaise, and cough. Note that this is part of routine surveillance for Covid-19 in health workers at the United States site. Consent forms will ask for consent to access this survey information.

Any positive response on the survey will trigger a nasopharyngeal, oral and/ or rectal swab to be collected to test for Covid-19 via rt-PCR

All participants, regardless of survey responses, will have serology for Covid-19 tested at 4 week intervals during the follow-up period (6 months)

If a participant completes the follow-up period and does not test positive for disease, their study participation is complete

If a participant does test positive for disease, their disease status will be ascertained for up to two months or until an outcome is available through one of the following mechanisms: (1) an electronic survey if they are not admitted to the hospital, including questions about the number of days they are ill, daily fever, and other symptoms; or (2) if they are admitted to the hospital, ordinal outcomes for disease severity will be extracted from the hospital's electronic medical records system.

During the first week of follow-up, all participants will actively be asked about any adverse events; thereafter, participants will report unsolicited AEs through the electronic survey. Vaccine related adverse events will be graded using the FDA guidance (<https://www.fda.gov/media/73679/download>) and noted using WHO-recommended Adverse event following Immunization forms (AEFI; <https://vaccine-safety-training.org/classification-of-aefis.html>).

Participants will have the option of donating 12 mL of blood for plasma (serology) and PBMCs for secondary analysis of immune correlates and for future analysis based on covid19-specific IgM and IgG. If they do not donate 12mL of blood, a fingerstick will be required for baseline COVID19 serology.

Dried Blood Spot (DBS): all participants will self-collect DBS samples at week 4, 8, 12, 16, 20 and 24. Envelopes to store the DBS are provided upon enrollment and can be mailed or dropped off at work and picked up by study coordinators.

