10. SAMPLE SIZE AND STATISTICAL ANALYSIS

Data will be reported quantitatively. All analyses will be performed from the intention-to-treat principle. Missing data will be dealt with by multiple imputation using the mice package in R.

a. Sample size calculation

The study in the United States will include at least three sites: Houston (BCM and MD Anderson Cancer Center considered as 'one site' due to proximity), Texas A&M University (TAMU), and Cedars Sinai Medical Center (CSMC). TAMU will enroll 1400 individuals. The proposed enrollment sample size is designed to provide 80% power to detect a 60% vaccine efficacy (a relative risk of 0.4 among the vaccinated). This is based on the observed three-fold decline in respiratory infections in the South Africa adolescent cohort with 80% power and 0.05 type 1 error in a two-tailed test. We expect 5% of study participants to develop symptomatic COVID19 during follow-up, therefore a sample size of 1400, with 700 receiving intervention and 700 receiving placebo. We do not expect significant loss to follow up among HCWs (there has been zero LTF after the first 500 participants). We will plot Kaplan-Meier curves comparing COVID19 disease between the BCG and placebo groups and report hazard ratios and p-values using Cox proportional hazard models. DBS samples will be collected at baseline and weeks 4, 8, 12, 16, 20 and 24 post intervention. PBMCs and plasma donations are optional at baseline, 12 and 24 weeks. If interim analysis identifies a large proportion of participants to be seropositive before intervention, power analysis will be evaluated and an amendment will be submitted if additional participants need to be recruited.

b. Interim analysis

One month after the first 100 participants are enrolled, an interim analysis will be held by the independent statistician of the trial. Data will be exported independently from all sites and then data collated and merged for the interim analysis). The above described statistical analysis will be evaluated as well as safety profile. Enrollment is expected to occur within the first two months of launch. Interim analysis will occur based on study enrollment and three to six interim analysis will occur based on temporal dynamics of enrollment as requested by the DSMB. We will stop the clinical trial early if the p-value of any interim analysis is smaller than the pre-specified type-1 error cutoff. Each interim analyses will be reported to the DSMB.

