c. Primary study parameter(s)

The primary endpoint, development of COVID19 infection, we will use the Cox proportional-hazards model to calculate hazard ratios for the development of Covid-19. This will be reported as the proportion of individuals receiving the intervention who are PCR-positive or seroconvert.

d. Secondary study parameter(s)

Disease severity as discussed above and based on guidelines proposed by the World Health Organization. We will use the Chi square for significance to calculate the risk ratios for the development of severe Covid-19 disease. Disease severity will be based on the level of care required for individuals who test positive for COVID19 as follows: non-hospital-based care; patient hospitalized but no oxygen required; hospitalized and oxygen required; patient treated in intensive care and/or on mechanical ventilation; patient died. Additional WHO criteria for severity include severe pneumonia, respiratory failure, acute respiratory distress syndrome, sepsis and septic shock. Days absent will also be self-reported via the RedCap Research App. Immunology and epigenetic studies for innate training be implemented, but in brief, immune cells will be stimulated with non-specific (LPS, mitogen, BCG) and COVID19-specific antigens with immune function measured by ELISA and flow cytometry. Epigenetic studies are discussed in more detail below.

e. Other study parameters

Continuous baseline characteristics will be reported as mean and standard deviation or median and inter-quartile range, as appropriate. Categorical baseline characteristics will be reported as count and percentage. No statistical testing for baseline characteristics will be performed.

f. Synthesis

In this trial, the BCG vaccine will be used in hospital personnel during the epidemics to prevent infection with the new SARS-CoV-2 virus. The risk of the BCG vaccine is very well known (see product inserts) and only minor local side effects (redness, local pain) are common. The benefits of BCG vaccination based on earlier clinical studies are expected to be a reduction in infection and morbidity of at least 25% compared to unvaccinated individuals, and potentially much higher. These effects are mediated by the capacity of BCG to induce trained immunity and may represent an important tool for protection against SARS-CoV-2 virus infection until a specific effective vaccine is developed.

g. Epigenetic and Immune Corollary Studies

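### Severity is recorded on five ordered care levels but tested as an undefined proportion 'severe' by chi-square, so the ordering is lost and the result depends on a cut the plan never states

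*Combined protocol and SAP*

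**What the plan says.** Section 6.b sets the secondary endpoint, among participants who test positive, as "the proportion with severe disease following BCG vaccination compared to placebo, as defined by the following necessary care levels". Five levels follow, in order: care outside hospital; hospital without oxygen; hospital with oxygen; intensive care and/or ventilation; death. Sections 4.c and 10.d repeat the list and add further WHO severity criteria without tying them to it.

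Section 7.c treats the data as ordered: for admitted participants, "ordinal outcomes for disease severity will be extracted from the hospital's electronic medical records system".

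The analysis in section 10.d is binary: "We will use the Chi square for significance to calculate the risk ratios for the development of severe Covid-19 disease". No trend, rank or proportional-odds analysis appears anywhere in section 10. No section says where on the scale severe begins. The halting rules in section 9.d list conditions that make COVID-19 illness severe (severe pneumonia, respiratory failure and similar) but do not map them to the care levels.

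Mitigating severity is the only numbered secondary objective in section 2. Section 10.h names a further secondary objective, on immune correlates.

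**The concern.** A risk ratio for severe disease needs a two-way split. With the split at oxygen, a death counts the same as oxygen therapy, and admission without oxygen counts the same as staying at home. Even if section 10.d were read as a chi-square on the full two-by-five table, that test would also ignore order.

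Two things are at stake. First, the plan's inputs imply few infections, and a cut above hospitalisation leaves only a handful of severe events. A shift across the recorded care levels could then go unreported. Second, because the cut is not stated, it could be chosen after the data are seen, and the result depends heavily on it.

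**Working it through.** **The plan's own figure.** The documents give no power for severity. The only stated figure is for the primary endpoint: "designed to provide 80% power to detect a 60% vaccine efficacy (a relative risk of 0.4 among the vaccinated", with "0.05 type 1 error in a two-tailed test" and 1,400 participants. With 5% v 2%:

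n per arm = [1.96·√(2·0.035·0.965) + 0.8416·√(0.05·0.95 + 0.02·0.98)]² / 0.03² ≈ 588, or 653 with continuity correction.

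This does not reproduce 700 per arm. It errs on the conservative side and does not bear on the severity analysis.

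**Number of infections.** Section 10.a gives the event rate this way: "We expect 5% of study participants to develop symptomatic COVID19 during follow-up". It allots the 1,400 equally, 700 to each arm, and allows nothing for dropout.
- If 5% is the placebo rate: 700 × 0.05 = 35 placebo and 35 × 0.4 = 14 BCG, 49 in all.
- If 5% is the overall rate: 1,400 × 0.05 = 70, split 50 v 20.
- If seroconversions also count (section 10.c), infections could be more numerous; 105 v 42 (three times 35 v 14) is an illustration.

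**Assumptions not in the documents.** The placebo split over the five levels is taken as 80/8/6/5/1% or 70/12/10/6/2%. The common odds ratio for worse severity is 0.4. The 0.4 in section 10.a is a relative risk for infection, not severity. The only severity rates given (section 1) come from a hospitalised cohort and include no oxygen rate.

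**Why the cut matters.** Under an odds ratio of 0.4, oxygen-or-worse falls as follows:
- From 12%: odds 0.12/0.88 × 0.4 = 0.0545, which is 5.2%. Expected events: 35 × 0.12 = 4.2 placebo and 14 × 0.052 = 0.7 BCG.
- From 18%: odds 0.18/0.82 × 0.4 = 0.0878, which is 8.1%. Expected events: 6.3 and 1.1.

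With no BCG events, 8 of 35 in placebo gives z = 0.2286/√(0.1633·0.8367·0.1) = 1.956, just short of 1.96. Nine gives z = 2.10. So chi-square needs at least nine severe placebo cases and none on BCG, well above what is expected.

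**Simulated power** (40,000 runs, odds ratio 0.4, two-sided 0.05, rejections in BCG's favour, tie-corrected Wilcoxon v uncorrected chi-square):

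| BCG v placebo infections | Not hospitalised | Wilcoxon, 5 levels | Chi-square: any hospitalisation | Chi-square: oxygen or worse | Chi-square: ICU or worse |
|---|---|---|---|---|---|
| 14 v 35 | 80% | 7.2% | 7.0% | 0.9% | 0.0% |
| 14 v 35 | 70% | 16.4% | 15.3% | 5.2% | 0.1% |
| 20 v 50 | 70% | 24.7% | 25.7% | 13.9% | 0.8% |
| 42 v 105 | 80% | 34.5% | 35.7% | 20.2% | 3.7% |
| 42 v 105 | 70% | 50.3% | 49.8% | 32.6% | 9.4% |

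At the oxygen cut the gain is 6.3 and 11.2 points (14 v 35), 10.8 (20 v 50), and 14.3 and 17.7 (42 v 105). Against the hospitalisation cut the rank test lies between 1.2 points below and 1.1 above.

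**Like for like with exact tests, 14 v 35, oxygen cut.** Fisher 1.1% and 5.4% v permutation Wilcoxon 4.7% and 14.4%: gains of about 3.5 and 9 points. Under no effect the permutation Wilcoxon rejects in 4–5%.

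**Sensitivity.**
- Odds ratio 0.75, 14 v 35: gain of about 2 to 3 points at the oxygen cut.
- About 10% of infections hospitalised, 14 v 35: no useful power for any test and no gain.
- 42 v 105 with all the added infections at the lowest level (the odds ratio applied to the diluted split): gains fall to about 5 and 11 points.
- Over a wider set of splits and infection counts, the oxygen-cut difference ran from about −1 to 33 points at odds ratio 0.4 and from −1 to 4 at 0.75. At a hospitalisation cut it stayed within about 3 points either way.

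**The case against.** The strongest reply is that the loss comes from an assumed cut. The plan never says oxygen-or-worse, and a two-by-two test at any hospitalisation performs as well as the five-level test. On this view the real defect is the missing definition of severe, and a risk ratio is easier to interpret than a common odds ratio. This stands in part. The missing definition is a defect in its own right, and the fix includes it. But section 9.d associates severe illness with conditions more serious than admission alone, so the hospitalisation cut cannot be presumed. A test on all levels gives up about 1 point at most against that cut in the runs tabulated and avoids the large losses at higher cuts.

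It is also fair that a severity odds ratio of 0.4 has no source in the plan. The only figure that mentions morbidity, in section 10.f, is a reduction of at least 25% and potentially much more. Taken as an odds ratio near 0.75, it makes the gain small.

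A reader might infer that the plan forfeits a fixed number of power points. The documents do not support that: the cut, the severity split and the severity effect are all unstated. A reader might also infer that an ordinal test would make the endpoint adequately powered. It would not: at 14 v 35 the permutation test still misses the assumed effect about 86–95% of the time.

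These figures condition on infection, a subset formed after randomisation. Which participants should be analysed is a separate question that this point does not settle.

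**Conclusion.** The concern holds as a cheap improvement to the analysis. The plan records an ordered outcome, calls it ordinal, and discards the order in favour of a dichotomy it never defines. The benefit is conditional. With 20–30% of placebo infections hospitalised, a common odds ratio of 0.4 and an oxygen-or-worse cut, it is about 6 to 11 points at 14 v 35 infections (about 3.5 to 9 with exact tests). It is about 14 to 18 points at 42 v 105 with the same split, and less if the added infections are mostly asymptomatic. It is about 2 to 3 points at an odds ratio of 0.75, and essentially nil if severe means any hospitalisation or if only about 10% of infections are hospitalised at 14 v 35. The firmer gain is that the main severity test would no longer depend on an unstated cut. With about 49 infections, a non-significant severity result should not be read as evidence of no effect under either method.

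**What to change.** In sections 6.b and 10.d:
- Make the severity test a permutation Wilcoxon (or proportional-odds) test of the worst care level reached. Report the common odds ratio, its 95% confidence interval and a table of counts per level by arm.
- State which care levels count as severe and how the added WHO criteria relate to them. Keep the severe/not-severe risk ratio as a descriptive summary.
- Apply this in whichever severity analysis set is finally adopted.

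A single ordinal test over all 1,400 with uninfected as the lowest level is not a substitute. In simulation with an infection effect present and the 80% split, its power was 87.1% with no severity effect and 87.9% with a severity odds ratio of 0.5, so it mainly measures infection.

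The cost is a change of wording and one extra analysis on data already collected. The drawback is that a common odds ratio is harder to explain than a risk ratio, and its value as a summary (though not the Wilcoxon test itself) leans on proportional odds.

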COVID19 serology is currently being developed. When available (FDA approved test availability is rapidly evolving and improving), serology from blood drawn at baseline will be used to exclude individuals with preceding COVID19 infection from analysis.

To evaluate if the metabolic-epigenetic-immune mechanisms of the non-specific benefits of BCG for Covid19 are similar to that as previously described (Arts et al 2017), the collection of 12 mL of blood, in sodium heparin tubes, will be option to the participant. Blood will be processed for plasma (~4mL) and PBMCs. PBMCs will be cryopreserved and saved for future epigenetic (ATAC-seq, ChIP-seq, DNA methyl EPIC) and immune functional studies.

h. Flow cytometry based immune profiling

A secondary objective of this project is to elucidate the duration and immune correlate of protection of non-specific epigenetic-mediated immune “innate training” by BCG against Covid19. To do so, we will evaluate transcription regulation (DNA methylation, ATAC-seq, Chromatin immunoprecipitation), gene expression (reverse transcription PCR, RNA-seq) and immune phenotyping experiments (ELISAs) and multi-parameter immune phenotyping. We have developed multiple flow cytometry panels to measure the immune response. DNA methylation EPIC and other sequencing based arrays allow for genome wide evaluation of

epigenetic silencing. Genome wide evaluation will be validated with site-specific evaluation using PCR as previously described (DiNardo et al JCI 2020; 32125282). Flow cytometry-based immune phenotyping allows 18 parameters to simultaneously be measured. By first stimulating the PBMCs with viral or mycobacterial peptides, we are able to simultaneously **measure and correlate** the quantity and quality of the viral and/ or mycobacterial induced immune phenotype (CD4, CD8, CD36, CD14, CD23), transcriptional changes (T-bet, GATA-3, Foxp3, Helios) and functional immune response such as cytokine release (IL-2, IL-4, IL-10, TGF- β , TNF and IFN- γ) or effector function (perforin, CD107a). COVID19-specific viral peptide mixes are in development and the PBMCs will be saved for a time when measuring COVID19-specific immunity is feasible.

i. Epigenomic DNA methylation

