BCG induced non-specific immunity has been linked to chromatin conformation and DNA methylation. Therefore, these additional epigenetic studies will be evaluated as part of secondary analysis. The Illumina Infinium MethylEPIC array tests ~850,000 methylation sites including promoters, enhancers and non-island sites. Briefly, genomic DNA (gDNA) will be isolated (DNeasy protocol) from 1×10^6 PBMCs with >80% viability. From this quantity of PBMCs, I am able to retrieve >1.5 μ g DNA, which is sufficient to implement this assay (500ng). Experiments only proceed after strict quality control analyzing nucleic acid quality using a Qubit 3.0 fluorometer and Agilent 4200 Tape Station System. I will use the Zymo EZ DNA Methylation kit to bisulfite treat 500ng of gDNA prior to MethylEPIC testing. Methylation IDAT files will be imported into R statistical system using the Bioconductor (<http://www.bioconductor.org>) minfi package. After preprocessing and normalization, the Bioconductor limma package will identify probes with greater than 2 or less than 0.5-fold differential methylation with p-values < 0.05. Statistically significant differentially methylated probes will be visualized in Ingenuity Pathway Analysis. Gene ontology (GO) and Gene Set Enrichment Analysis analysis will be implemented using Molecular Signature Database (MSigDB) using hyper-geometric distribution that accounts for multiple comparisons. To evaluate if cell composition is confounding results and to determine the DNA methylation status of specific cell types (CD4, CD14, CD8, NK, and B cells), I will implement the bioinformatic pipelines EDEC (Epigenomic deconvolution) and MeDeCom (methylation decomposition). Both methods utilize linear algebra and classification techniques to quantify the DNA methylation profiles in several steps: 1) identifying optimal number of informative cell subpopulations 2) identify simultaneously both the estimated percentage of and the DNA methylation profile of each cell subpopulation. The explanatory cell subpopulations are then matched to DNA methylation profiles of known references via Spearman correlation. This approach offers multiple benefits: it enables us to assess DNA methylation changes in a cell type specific manner, but in a cost-effective approach because I will be profiling only the heterogeneous blood cells. Validation of bioinformatic EDEC results will then be carried out in magnetic bead purified cell types as described below.

j. ATAC-seq

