DNA hyper-methylation inversely correlates with chromatin accessibility, however other means of epigenetic silencing exists (i.e H3K27me3, etc.). Therefore to confirm that specific DNA hyper-methylation marks correlate with decreased chromatin accessibility, we will implement ATAC-seq, epigenome-wide chromatin accessibility evaluation. 1×10^5 cells of interest (identified after EDEC as described above) undergo cell lysis, Tn5-mediated transposition followed by DNA purification, PCR amplification, DNA quality Bioanalysis (using Agilent and Qubit as described above) and sequencing. Bioconductor packages will be used for preprocessing, normalizing and identification of differential chromatin accessibility defined as greater than 2 or less than 0.5-fold difference with p values < 0.05.

k. Benefits and risks assessment, group relatedness

The risk to and burden for the subject of BCG vaccination is estimated to be low, according to two previous trials that have been performed with BCG vaccines.[7, 11, 13] The beneficial effect BCG vaccination for the individualized participant is unknown, although the objective is to prevent severe illness to SARS-CoV-2 infection. Using an adaptive design, the study aims to find a positive effect of BCG-vaccine on a population level, which could be applied quickly in participants allocated to placebo and implemented to hospitals that do not participate in the study.

11. STRUCTURED RISK ANALYSIS**a. Potential issues of concern**

An extensive description of the mechanisms of action of the BCG vaccine, referring to the available in vitro and in vivo evidence, could be found in the Summary of Product Characteristics and the Product Insert.

a. Level of knowledge about mechanism of action

BCG activates NOD2 receptor pathway, and subsequently induces long-term epigenetic changes in chromatin of myeloid cells.[10, 13] The epigenetic reprogramming leads to increased antimicrobial activity of myeloid cells (cytokine production, phagocytosis, reactive oxygen species release). At the same time, BCG induces potent activation of cellular specific immunity, with strong induction of Th1 responses and IFNg release.

b. Previous exposure of human beings with the test product

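### Methylation probes (about 850,000) and ATAC-seq regions are called by a two-fold difference plus p<0.05 with no multiplicity adjustment stated, so the false-positive content of these lists is not controlled

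*Combined protocol and SAP*

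**What the plan says.** Section 10i (Epigenomic DNA methylation) gives the size of the screen: "The Illumina Infinium MethylEPIC array tests ~850,000 methylation sites". After preprocessing and normalization, the "limma package will identify probes with greater than 2 or less than 0.5-fold differential methylation with p-values < 0.05". The next sentence treats the probes that pass as established findings: "Statistically significant differentially methylated probes will be visualized in Ingenuity Pathway Analysis".

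Multiplicity is mentioned once in these sections. It is attached to the gene ontology and gene-set step, which is run "using hyper-geometric distribution that accounts for multiple comparisons".

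Section 10j (ATAC-seq) uses the same rule, with Bioconductor packages used for "identification of differential chromatin accessibility defined as greater than 2 or less than 0.5-fold difference with p values < 0.05". It does not say how many regions will be tested.

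Section 10h adds a later check: "Genome wide evaluation will be validated with site-specific evaluation using PCR". Section 10i also plans to validate the cell-deconvolution results in purified cells. No general statement elsewhere in section 10 adjusts p-values at probe or region level.

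**The concern.** With hundreds of thousands of simultaneous tests, an unadjusted 0.05 threshold bounds the error for each probe but says nothing about what share of the resulting list is false. Here that list is labelled significant and passed to pathway analysis to address the trained-immunity mechanism. An adjustment across gene sets comes after the list has been formed and cannot correct it.

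The two-fold requirement does remove null probes. How many it removes depends on sample size and noise, not on an error level that anyone has chosen. At stake is the credibility of the epigenetic findings. ATAC-seq, which is meant to corroborate the methylation marks, shares the weakness.

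**Working it through.** **Inputs from the plan.** Number of probes m = 850,000 (section 10i). Threshold α = 0.05 and fold change above 2 or below 0.5, that is |log2 difference| > 1 (sections 10i and 10j).

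**Not in the plan.** Samples per arm (donation is optional under section 10a), between-person SD, the scale of the fold change, sidedness, and the number of ATAC-seq regions. The values of n and SD below are assumptions, and tests are taken as two-sided. The plan states no error rate for these lists, so there is no figure of its own to reproduce.

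**Step 1: p criterion alone, no true differences.** Expected false calls = m x α = 850,000 x 0.05 = 42,500. For scale, Bonferroni control at 0.05 would need p < 0.05/850,000 = 5.9 x 10⁻⁸.

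If a fraction π of probes truly differs and power is w, the expected share of false calls is about (1−π)α / [(1−π)α + πw]. With π = 1% and w = 0.8 there are 850,000 x 0.99 x 0.05 = 42,075 false and 850,000 x 0.01 x 0.8 = 6,800 true calls, so 42,075/48,875 = 86% are false. Over w from 0.5 to 1.0 the share is 98–99% for π = 0.1%, 83–91% for π = 1% and 49–66% for π = 5%. These shares ignore the two-fold filter.

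**Step 2: both criteria, no true differences.** Take normal log2 values with SD σ, n per arm and a pooled two-sample t-test. The standard error is σ√(2/n). Given the sample SD s, a null probe passes when its absolute difference exceeds max(1, t₀.₉₇₅ · s√(2/n)). So

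P = E_s{ 2[1 − Φ( max(1, t₀.₉₇₅ · s√(2/n)) / (σ√(2/n)) )] },

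integrated over the distribution of s on 2n − 2 degrees of freedom. For σ = 1.0 and n = 10, P = 0.0221. Expected false calls, 850,000 x P:

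| Assumed log2 SD | n=5 per arm | n=10 | n=20 | n=50 | n=100 |
|---|---|---|---|---|---|
| 0.5 | 1,291 | 7 | 0 | 0 | 0 |
| 1.0 | 35,065 | 18,796 | 1,331 | 0.5 | 0 |
| 1.5 | 41,892 | 41,177 | 26,791 | 729 | 2 |

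The ordinary t-test stands in for limma's moderated test, so these counts are indicative.

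**Step 3: simulation check.** Three runs of 850,000 null probes each gave 18,801–18,924 calls (SD 1.0, n=10), 41,150–41,595 (SD 1.5, n=10), 1,202–1,253 (SD 0.5, n=5) and 719–779 (SD 1.5, n=50), close to the table. Benjamini-Hochberg at 0.05 plus the two-fold filter gave 0 or 1 call in every run.

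**Step 4: the fold change taken on methylation proportions (beta values).** With 200,000 null probes, the share passing both criteria was:

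- mean 0.03, SD 0.02: 3.5% (n=5), 1.8% (n=10), 0.1% (n=20), 0% (n≥50);
- mean 0.05, SD 0.05: 4.0% (n=5), 4.2% (n=10), 2.7% (n=20), 0.06% (n=50), 0% (n=100);
- means 0.2, 0.5 and 0.8 with SDs 0.05, 0.1 and 0.05: at most 0.002% at any n from 5 to 100, or 850,000 x 0.00002 = 17 probes if every probe behaved that way.

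On this scale the problem is confined to low-methylation probes in small groups. The choice of scale therefore matters, and the plan does not make it.

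**The case against.** The strongest reply is that this is an outline for a discovery screen on banked cells. Section 10g saves the cells for future assays, donation is optional, and the formal objectives (section 2) and endpoints (section 6) contain no epigenetic outcome. The p-value may have been meant as adjusted. The two-fold filter may do most of the work: in the log2 scenarios about 2 or fewer false calls remain at n=100 per arm, and on the beta scale mid-range probes almost never pass. PCR, purified cells and ATAC-seq give later cross-checks. A random probe list would not be expected to favour particular pathways, apart from probe correlation and unequal numbers of probes per gene.

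Much of this stands as a limit on weight. The per-probe error rate is nominally at most 5%; what is not fixed is the false-discovery or family-wise rate of the list. The figure of 42,500 is an upper reference and not a forecast.

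It does not remove the point. The plan states a concrete rule, calls the result significant, and specifies a correction at the gene-set step but not at the probe step. Later checks on selected sites, with no stated selection rule, do not set the error rate of the list. If adjusted values were intended, saying so costs nothing and prevents a choice made after seeing the data.

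**Conclusion.** The concern holds, as a minor one. Followed as written, the rules in sections 10i and 10j fix neither the false-discovery rate nor the family-wise rate of the probe and region lists. With no true differences, expected false methylation calls range from almost none to nearly 42,000, depending on assumed group sizes of 5 to 100 per arm, assumed log2 SDs of 0.5 to 1.5, and the fold-change scale. The large counts need small groups or noisy probes. No count can be given for ATAC-seq because the number of regions is not stated. The primary efficacy and safety conclusions are not affected.

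**What to change.** In section 10i, replace the p criterion with a Benjamini-Hochberg adjusted p-value (false-discovery rate) below 0.05 across all tested probes. In section 10j, do the same across all tested regions. Keep the two-fold threshold as an additional effect-size filter and state whether it applies to beta values or to log2/M-values. Run pathway analysis on the list that passes. Alternatively, run the gene-set enrichment analysis already named in 10i on the full ranked list; the hypergeometric test needs a selected list, so that option should be written out separately.

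The cost is one sentence in each of two sections, with no new data or assays. limma is already named in 10i; 10j names only Bioconductor packages, so the package used there should be stated too. The downside is that fewer sites will be declared significant and some true but small differences will be missed. The rule should be fixed before the banked samples are analysed.
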